The proposed study would be an 8-week, randomised, controlled, parallel-group, clinical trial which will be conducted at the Inpatient and Outpatient settings of the Department of Psychiatry, AIIMS, Bhubaneswar. Patients with the diagnosis of Post Schizophrenic Depression according to the ICD 10 (DCR) and meeting all the Inclusion and Exclusion Criteria would be selected for the study. At first, the patients and their family members/ guardians would be explained about the study procedure along with its possible risks and benefits using a Patient Information Sheet (in their local language). After obtaining a written Informed Consent from the Legally Authorised Relative, the patients would be finally recruited for the study.

All recruited patients would be randomized using computer-generated random numbers into two treatment groups with an allocation ratio of 1:1. The sociodemographic and clinical data of the patients would be collected as per the designed sheets. Then at baseline, the CDSS and CGI ratings would be assessed, and the serum BDNF would be tested for each patient. The study would be rater-blinded. The experimental group would receive Amisulpride at a low dosage of 100-300 mg/day and the control group would receive a combination of Olanzapine at 5mg or 10 mg/day and Fluoxetine at 20mg/day.

The two groups would be followed for 8 weeks, at the completion of which all the patients would be reassessed. The follow-up assessment would involve a re-evaluation of the CDSS and the CGI scores and the Serum BDNF levels to see for any change. The data thus collected would be analysed, compared within and in between the study groups and statistical tests would be applied for drawing conclusions.

RANDOMIZATION:

All recruited patients will be randomized by computer-generated random number into two treatment groups with an allocation ratio of 1:1.

BLINDING:

The proposed study will be rater-blinded. The ratings of the CDSS and CGI scales would be done by a psychiatrist who would be blinded to the nature of the intervention provided.

FOLLOW UP:

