5. The missing values would be replaced by the help of multiple imputations for conducting an Intention to Treat (ITT) analysis and the pooled data would be used for further analysis
6. All the statistical analyses would be performed using SPSS 23.0 (IBM, NY USA)
7. For obtaining statistically significant results, P value would be set at < 0.05

SAMPLE SIZE CALCULATION:

A sample size of 26 per group will achieve a power of 80%, to detect a difference of 3 in Calgary Depression Scale for Schizophrenia (CDSS) between the groups with known SD of 3.8 and with a significant level 0.05 using a Two-sided Two-sample T-test. Assuming attrition of 10-15% 30 patients in each group will be recruited.

Sample size calculation was done by PASS software (Version 11)

EXPECTED OUTCOME:

- The role of low dose Amisulpride in the treatment of Post Schizophrenic Depression can be explored for the first time (as no study has been done on it yet)
- Low dose Amisulpride is expected to be more efficacious than Olanzapine-Fluoxetine combinations in PSD. If this comes true, a new treatment strategy in PSD would be obtained.
- Use of Amisulpride in PSD would have the following advantages:
 1. Polypharmacy in PSD patients can be avoided
 2. Overall reduction in the medical expenditure of the patients
 3. Duration of treatment would not be an issue as in the case of treatments with antidepressants
 4. In advent of positive symptoms simply hiking the Amisulpride doses to higher dose range can treat the patients, without switching to any other antipsychotic.
 5. Lesser risk of side-effects in the patients, as Amisulpride is a relatively safer drug among other antipsychotics

ETHICAL ISSUES:

1. All works under the proposed study would begin only after obtaining approval from the Institutional Ethics Committee, AIIMS Bhubaneswar
2. All the patients and their family members/ guardians would be adequately explained, in the language they understand, about the study procedure and the possible risks and benefits associated with it. Only those patients with a written Informed Consent from the Legally Authorised Relative would be enrolled for the study.
3. Strict confidentiality would be maintained about the identity, sensitive information and personal details of the patients obtained during the course of the study.
4. Any patient can willfully withdraw his/ her participation at any point during the course of the study.

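### The primary between-group comparison is unadjusted, although baseline CDSS and inpatient/outpatient setting are available for every patient at no cost

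*Combined protocol and SAP*

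**What the plan says.** **Analysis.** Item 3 of the Statistical Analysis Plan compares the group means by an unpaired t-test or a Mann-Whitney U test. No item names a covariate. Under Follow Up, the size of the change is to be compared between groups, and the null hypothesis also concerns change in CDSS.

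**Data in hand.** Under Methodology, CDSS is rated at baseline in each patient, after randomisation is described, and again at 8 weeks. The study is "which will be conducted at the Inpatient and Outpatient settings of the Department of Psychiatry", and Inclusion Criteria admit patients from both settings. Setting is therefore known when a patient enters.

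**Randomisation.** The Randomization section is one sentence: "All recruited patients will be randomized by computer-generated random number into two treatment groups with an allocation ratio of 1:1". Methodology says much the same. Neither place states a restriction, a stratification factor, who holds the list or how it is concealed. Under Blinding, only the rater is blinded.

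**Sample size.** "A sample size of 26 per group will achieve a power of 80" per cent, "to detect a difference of 3 in Calgary Depression Scale for Schizophrenia (CDSS) between the groups with known SD of 3.8", "with a significant level 0.05 using a Two-sided Two-sample T-test". Then: "Assuming attrition of 10-15% 30 patients in each group will be recruited".

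**The concern.** The sample size leaves little margin. The plan is sized for about 80% power after attrition, and the test it names puts all between-patient variation into the error term. Part of that variation may be explained by two quantities the trial already has: where a patient started on the CDSS, and whether the patient was an inpatient or an outpatient.

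Two things are at stake. One is precision: any variance these covariates explain is power forgone. The other is chance imbalance: with about 30 per arm, the groups can differ noticeably at baseline, and an unadjusted test carries that difference into the estimate. Comparing change scores deals with baseline CDSS only in part, because subtracting the baseline fixes its coefficient at 1 when the data may call for less. Setting is not dealt with at all.

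**Working it through.** **Inputs from the plan.** Difference 3, SD 3.8, two-sided alpha 0.05, power 80%, 26 per group, 30 recruited per group, attrition 10-15%.

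**1. The plan's own figure.**
- Normal formula: n = 2 × (1.960 + 0.842)² × 3.8² / 3² = 25.2, rounded up to 26 per group. The stated figure is reproduced.
- Power at 26 per group from the noncentral t distribution is 79.7%.
- After attrition, 30 × 0.90 = 27 and 30 × 0.85 = 25.5 per group, so the trial would be analysed at about that size.

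**2. Gain from adjusting for setting (assumed values).** Let p be the inpatient share and g the difference between settings in CDSS outcome. Taking 3.8 as the total within-group SD, setting explains R² = p(1 − p)g² / 3.8², and the residual SD is 3.8 × √(1 − R²). Power at 26 per group:

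| p (assumed) | g = 1 | g = 2 | g = 3 |
|---|---|---|---|
| 20% | 80.2% | 81.5% | 83.7% |
| 30% | 80.3% | 82.0% | 84.9% |
| 50% | 80.4% | 82.5% | 86.0% |

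Example: p = 0.5, g = 3 gives R² = 0.25 × 9 / 14.44 = 0.156, residual SD 3.49, power 86.0%. The degree of freedom spent on the covariate costs less than 0.1 point.

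**3. Gain from adjusting for baseline CDSS (assumed correlation).** The plan gives no correlation ρ between baseline and week-8 CDSS, and does not say whether 3.8 is the SD of a score or of a change. I take ρ = 0.3 to 0.6 as an illustration.
- If 3.8 is the SD of the week-8 score, the residual variance is multiplied by 1 − ρ². At ρ = 0.3 the SD is 3.8 × √0.91 = 3.62 and power is 83.3%. At ρ = 0.6 it is 3.8 × √0.64 = 3.04 and power is 93.7%.
- If 3.8 is the SD of change, with equal SDs at both visits, the factor relative to the change score is (1 − ρ²) / [2(1 − ρ)] = (1 + ρ)/2. At ρ = 0.3 the SD is 3.8 × √0.65 = 3.06 and power is 93.3%. At ρ = 0.6 it is 3.8 × √0.80 = 3.40 and power is 87.7%.

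**4. Chance imbalance in setting (assumed share).** With 30 per arm and m inpatients among 60, the number X in one arm is hypergeometric. A gap of 20 percentage points is 6 patients, so the probability is P(|2X − m| ≥ 6): 10%, 16% and 20% for m = 12, 18 and 30. If arm sizes and the number of inpatients also vary by chance, it is about 5% to 13%. A 20-point gap shifts the unadjusted difference by 0.20 × g, which is 0.2, 0.4 or 0.6 points for g = 1, 2 or 3.

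**5. Arm sizes, if randomisation is simple.**
- P(exactly 30:30) = C(60,30) / 2⁶⁰ = 10.3%.
- P(smaller arm 25 or fewer) = 2 × P(X ≤ 25) = 24.5%.
- Average power with 60 analysed is 84.6%, against 85.2% at exactly 30:30. With 52 analysed it is 78.9%, against 79.7%. A 26:34 split still gives 84.6%.

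The cost of unequal arms is 0.6 to 0.8 points of power.

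**The case against.** Randomisation makes the unadjusted comparison unbiased on average, so the planned test is valid. Nothing in the documents shows that CDSS change differs by setting: both settings belong to one department and share the same eligibility limits. The inpatient share, setting effect and baseline correlation are all assumed, and at the low end of the range the gain from setting is about half a point of power. Leaving a single-centre trial of 60 unstratified is a reasonable choice. All of this stands, and it limits the point to an improvement. It does not argue against adjusting, because the covariates are already collected.

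A reader might infer two stronger things from the randomisation text.

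- **That 30 per group cannot be reached, or that the last allocations will be predictable.** The documents never say that randomisation is simple or that an arm closes at 30. A computer-generated list of 30 + 30, or permuted blocks, fits the same sentence. The 30 can also be read as a planning target inflated from 26. Closing an arm at 30 under coin-tossing would leave 60 × 0.1026 = 6.2 allocations fixed on average, but no such procedure is described. Under a pre-generated 30 + 30 list, the closing run of identical allocations averages 60/31 = 1.9. In either case allocations are foreseeable only to someone who knows the scheme and the past assignments.
- **That pooling inpatients and outpatients biases the result.** It does not on average. It only permits chance imbalance and some loss of precision.

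**Conclusion.** The point holds as an improvement in efficiency that costs nothing. The between-group test ignores baseline CDSS and setting, and adjusting for both is the better method using data already in hand.

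The gain from setting alone is 0.5 to 6.3 points of power at 26 per group (79.7% to 80.2-86.0%), under assumed shares of 20-50% and assumed effects of 1-3 points. The gain from baseline CDSS may be larger but rests on an assumed correlation. If neither covariate predicts outcome, the loss is negligible.

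The unstated type of randomisation and concealment is missing detail. It is worth stating, particularly because only the rater is blinded. It is not evidence of a faulty allocation and not a sample-size error: even under simple randomisation the power cost is under 1 point, and the planned 26 per group reproduces.

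**What to change.** **Analysis.** Replace item 3 of the Statistical Analysis Plan, for the primary outcome, with an ANCOVA of week-8 CDSS on treatment, with baseline CDSS and setting at entry as covariates. Report the adjusted difference with its 95% confidence interval. Using change in CDSS as the response gives the same treatment estimate once baseline is in the model. Put both covariates in the multiple-imputation model of item 5 as well, and keep the unadjusted test as a sensitivity analysis. Fix this before the data are compared by group.

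**Randomisation.** If the list is not yet generated, state permuted blocks of varying, undisclosed size, stratified by setting, and name who holds the list and how it is concealed from recruiters. Incomplete blocks in two strata may leave the arms slightly off 30:30, which the figures above show is harmless. If the list already exists, state how it was generated and concealed.

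**Cost.** A few sentences, two model terms and possibly a new list. No extra patients, visits or measurements are needed.

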To compare the efficacy and safety of low dose Amisulpride Versus Olanzapine-Fluoxetine Combination and in patients with Post Schizophrenic Depression.

STUDY OBJECTIVES:**PRIMARY OBJECTIVES:**

1. To evaluate the change in the severity of depression in terms of change in Calgary Depression Scale for Schizophrenia (CDSS) scores in the study groups over 8 weeks

SECONDARY OBJECTIVES:

1. To evaluate the change in symptom severity and improvement in terms of change in Clinical Global Impression (CGI) scores in the study groups over 8 weeks
2. To evaluate the change in serum BDNF levels in the study groups over 8 weeks
3. To determine the correlation (if any) between the changes in CDSS scores, CGI scores and serum BDNF levels
4. To detect adverse drug reactions (if any) and grading their severity

MATERIALS AND METHODS**STUDY SETTING:**

The proposed study will be conducted at the Out-Patient (OP) and the In-Patient (IP) settings of the Department of Psychiatry, All India Institute of Medical Sciences, Bhubaneshwar.

STUDY DESIGN:

The proposed study will be a randomized, rater-blinded, controlled, clinical trial

STUDY PERIOD:

The study will be conducted within the time frame of two years.

STUDY POPULATION:

The proposed study will be conducted on the patients diagnosed with Post Schizophrenic Depression of the catchment area pertaining to AIIMS, Bhubaneswar.

INCLUSION CRITERIA:

All patients coming for treatment at the OPD and IPD of the Department of Psychiatry fulfilling the following are included:

1. Patients with Post Schizophrenic Depression according to ICD10-DCR (International Classification of Diseases 10– Diagnostic Criteria for Research) (9).
2. Aged between 18 to 60 years of either sex
3. Patients with a positive score of less than 29 on the Positive and Negative Syndrome Scale (PANSS) (10)
4. Patients with a score of more than 6 on the Montgomery-Asberg Depression Rating Scale (MADRS) (11)
5. Patients without Extrapyramidal symptoms: a score of less than 3 on the Simpson-Angus Scale (12)
6. With Informed consent from the Legally Authorised Relative

EXCLUSION CRITERIA:

Patients with any one of the following are excluded from the study:

1. Patients with a medical or neurological disorder
2. Patients with a history of substance dependence
3. Patients with high suicidality
4. Patients with a past history of primary depression
5. Patients already on Olanzapine-Fluoxetine combination or Amisulpride

METHODOLOGY:

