All patients under the study will be followed for a period of 8 weeks from the start of the intervention. Then, the follow-up assessments will be done by rating the CDSS, and the CGI scales once again in each patient. Serum BDNF levels will be tested again. The data obtained will be compared within each group to find the change before and after the respective interventions. Thereafter, the magnitude of the changes will be compared in-between the groups to find out the efficacy and safety of one treatment over the other. All the results will be statistically tested to understand their significance.

OUTCOME MEASURES:**Primary Outcome Measure:**

1. Calgary Depression Scale for Schizophrenia (CDSS) [Time Frame: 8 weeks]

Calgary Depression Scale for Schizophrenia (CDSS) (13) scores will be used to measure the change in the severity of depressive symptoms in the study groups from baseline over 8 weeks. the total score ranges from 0 - 36. Higher scores represent higher severity of depression.

Secondary Outcome Measures:

1. Clinical Global Impression (CGI) [Time Frame: 8 weeks]

Clinical Global Impression (CGI) scores (14) will be used to measure the change in illness severity, global functioning and improvement in the study groups from baseline over 8 weeks.

- The Clinical Global Impression - Severity scale (CGI-S) is a 7-point scale [minimum: 1 and maximum 7]: Higher scores means higher severity of disease.
- The Clinical Global Impression - Improvement scale (CGI-I) is a 7 point scale [minimum: 1 and maximum 7]: Higher scores means more clinical improvement.

2. Serum BDNF Levels [Time Frame: 8 weeks]

The change in serum BDNF levels in the study groups over 8 weeks.

3. Correlation [Time Frame: 8 week]

Determine the correlation (if any) between the between changes in CDSS scores, CGI scores and serum BDNF levels

4. Adverse Drug Reactions [Time Frame: 8 weeks]
Detect adverse drug reactions (if any) and grading their severity

STATISTICAL ANALYSIS PLAN:

1. The CDSS scores, the CGI scores and the serum levels of BDNF, being continuous variables would be expressed as a mean \pm standard deviation (SD) / standard error of means (SEM)
2. The means would be compared within the group by two-sided paired t-test / Wilcoxon signed rank test
3. The means between the groups would be compared using unpaired t-test / Mann Whitney U test
4. Correlation analysis will be done between the CDSS ratings, the CGI scores and the serum BDNF levels.

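### Is the safety comparison left without a basis because the SAP names no between-arm method for adverse drug reactions?

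*Combined protocol and SAP*

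**What the plan says.** AIM states the purpose as "To compare the efficacy and safety of low dose Amisulpride Versus Olanzapine-Fluoxetine Combination". Secondary objective 4 is narrower: find adverse drug reactions and grade them. Secondary Outcome Measures, item 4, repeats this with an 8-week time frame: "Detect adverse drug reactions (if any) and grading their severity".

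FOLLOW UP describes repeating CDSS, CGI and serum BDNF at 8 weeks and comparing each within groups. It then says that "the magnitude of the changes will be compared in-between the groups to find out the efficacy and safety of one treatment over the other", and closes with "All the results will be statistically tested to understand their significance". METHODOLOGY also names only those three as follow-up assessments.

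In the STATISTICAL ANALYSIS PLAN, item 1 covers "The CDSS scores, the CGI scores and the serum levels of BDNF, being continuous variables". Items 2 and 3 compare means within and between groups, with rank tests as alternatives. Item 4 correlates the same three measures. Item 5 reads "The missing values would be replaced by the help of multiple imputations for conducting an Intention to Treat (ITT) analysis". Items 6 and 7 give the software and the threshold of P < 0.05. None mentions adverse reactions.

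EXPECTED OUTCOME lists, among the advantages of amisulpride, "Lesser risk of side-effects in the patients, as Amisulpride is a relatively safer drug among other antipsychotics". SAMPLE SIZE CALCULATION concerns CDSS only and ends "Assuming attrition of 10-15% 30 patients in each group will be recruited".

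**The concern.** A trial that sets out to compare safety and expects one drug to do better should say how that comparison will be made. Here the only between-group method is for means of efficacy and biomarker variables, and the one sentence that mentions a safety comparison rests it on those variables. The test, the denominator (all treated patients or completers) and the summary (any reaction or by grade) are left open and could be settled after the data are seen. In a trial of 30 per arm, such a choice could decide whether a safety advantage is called significant. Item 5 does not say whether imputation extends to reactions in patients who leave. The Simpson-Angus Scale and PANSS positive score are used at entry but not repeated, so extrapyramidal or psychotic worsening would show only as a reported reaction or through CGI.

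**Working it through.** **The plan's own figure.** SAMPLE SIZE CALCULATION gives a difference of 3, SD 3.8, two-sided 0.05 and 80% power. Then n = 2(1.960 + 0.842)² × 3.8² / 3² = 2 × 7.849 × 14.44 / 9 = 25.2, so 26 per group, as stated. Thirty per group fits 10-15% attrition: 26/0.90 = 28.9 and 26/0.85 = 30.6. None of this involves adverse reactions, so the point cannot affect it.

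The documents give no adverse-reaction rates. All counts and risks below are assumptions.

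**Choice of test.** Take 3/30 against 10/30.

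- Pearson, uncorrected: χ² = 60(3×20 − 10×27)² / (30×30×13×47) = 60 × 210² / 549,900 = 4.81, p = 0.028.
- With continuity correction: χ² = 60(210 − 30)² / 549,900 = 3.54, p = 0.060.
- Fisher exact: p = 0.057.
- Newcombe 95% interval: the Wilson limits are 3.5% to 25.6% for 3/30 and 19.2% to 51.2% for 10/30. The difference is 23.3 points, interval 2.3 to 42.4.

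This is a boundary case. Fisher and the corrected test fall on one side of 0.05; uncorrected Pearson and the Newcombe interval fall on the other.

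How often does this happen? I summed binomial probabilities over all 31 × 31 = 961 outcomes at 30 per arm for which Fisher and uncorrected Pearson fall on opposite sides of 0.05.

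| True risks | Disagree | True risks | Disagree |
|---|---|---|---|
| 10% v 30% | 12.8% | 20% v 20% | 2.7% |
| 10% v 35% | 11.6% | 10% v 10% | 4.5% |
| 10% v 40% | 9.1% | 30% v 40% | 4.5% |
| 20% v 40% | 9.5% | 20% v 30% | 5.3% |
| 20% v 50% | 9.6% | 10% v 50% | 3.5% |
| 30% v 50% | 9.2% | 10% v 60% | 0.7% |
| 30% v 60% | 10.2% | | |

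Disagreement is greatest where the gap is 20 to 30 points and power is middling. It is lower for gaps of 0 to 10 or of 40 to 50 points. Fisher and the continuity-corrected chi-square gave the same verdict in every one of the 961 tables.

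**Choice of denominator.** Attrition of 10-15% is 3 to 4.5 of 30. Suppose 4 patients leave the 10/30 arm, all four had a reaction, nobody leaves the other arm, and only completers are counted. The comparison becomes 6/26 against 3/30: 23.1% − 10.0% = 13.1 points, Newcombe −6.6 to 33.1, against 23.3 points on all 30. This is a worst case. If 4 leave each arm regardless of reactions, the expected completer counts are 10 × 26/30 = 8.67 of 26 (33.3%) and 3 × 26/30 = 2.6 of 26 (10.0%), and the difference stays at 23.3 points.

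**What naming a method would buy.** The simple 95% half-width for a risk difference at 30 per arm is 1.96√(2p(1−p)/30): 15 points if both risks are 10%, 25 points if both are 50%. Fisher power is 37% for 10% v 30%, 30% for 20% v 40% and 26% for 30% v 50%. With 3/30 v 9/30 the Newcombe interval is −0.5 to 39.0 points. Fixing the method in advance changes none of these figures.

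**The case for a change.** The strongest case for a change is textual. AIM and FOLLOW UP both promise a comparison, so the detect-and-grade wording of objective 4 is not the whole story. The general sentence on testing all results follows a list of CDSS, CGI and BDNF and supplies no method. Even a descriptive safety table needs a denominator and a grading scale, and a line or two written before the data are seen would remove any room to choose. All of that is correct, and patients may well leave because of reactions, so the direction of the completer example is plausible.

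What does not stand is the weight put on it. The hypotheses concern CDSS only, and no safety hypothesis is stated. The expected advantage refers to other antipsychotics in general and sits beside polypharmacy and cost; it is a rationale, not a planned test. The FOLLOW UP sentence echoes the aim's wording, and the separate outcome line for reactions shortly afterwards shows that the investigators did not mean to read safety off BDNF. On denominators, item 5 already commits the plan to intention to treat, which points to all randomised patients. A reaction recorded before a patient leaves is observed, so there is nothing to impute and no reason to discard it.

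Repeating the Simpson-Angus and PANSS positive ratings at week 8 would be new data collection that the plan never promised. Adjusting the Simpson-Angus score for its entry value would gain little, because INCLUSION CRITERIA, item 5, confines that value to below 3.

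**Conclusion.** The observation is right as far as it goes: the SAP has no line on adverse reactions, and one FOLLOW UP sentence is loosely worded. It is a gap that analysts fill sensibly. For an outcome collected by arm and graded, the ordinary report is the number and proportion of patients with any reaction and by worst grade in each arm, on everyone treated, read descriptively.

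The choice of test can flip a verdict, but at the risks examined it does so in at most about 13% of trials, and in 0.7% to 5.3% of trials outside gaps of 20 to 30 points. The denominator moves the result materially only if withdrawal is concentrated among affected patients in one arm and the analyst departs from the stated intention-to-treat approach. With intervals some 15 to 25 points either side, a non-significant result could not be read as equal safety under any method, and a single significant p-value would be weak support for superiority.

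These sizes rest on assumed event rates and 30 patients per arm. The CDSS analysis and the sample size do not depend on the point. No change to the plan is called for.

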COVER PAGE

TITLE:

Efficacy and safety of low dose Amisulpride Versus Olanzapine-Fluoxetine Combination in the treatment of Post Schizophrenic Depression: A Randomised Controlled Trial

NCT04876521

DATE: June 1, 2019

STUDY PROTOCOL, STATISTICAL ANALYSIS PLAN & INFORMED CONSENT FORM

STUDY PROTOCOL

FULL TITLE:

Efficacy and safety of low dose Amisulpride Versus Olanzapine-Fluoxetine Combination in the treatment of Post Schizophrenic Depression: A Randomised Controlled Trial

BRIEF TITLE:

Low Dose Amisulpride Vs Olanzapine-Fluoxetine Combination in Post-Schizophrenic Depression (PSD-AOFC)

SCIENTIFIC BACKGROUND:

About one-fourth of patients who have schizophrenia ultimately develop post-schizophrenic depression (PSD) with higher morbidity and mortality risks, including a higher number of suicides (1-2). Studies regarding the pharmacological treatment options for PSD are scarce. Very few clinical trials have been conducted with antipsychotics involving small study samples (3-4). Moreover, antipsychotics are Serotonin-Dopamine Antagonists, an action opposite to that of antidepressants (5), so their exact role in treating PSD needs further exploration. Antidepressants have been used in schizophrenia with depression but have shown little success (6). An antipsychotic along with an antidepressant (like an olanzapine-fluoxetine combination, OFC) is now the commonly practised treatment strategy in PSD. However, there is insufficient evidence in the literature confirming its rationality.

Studies have shown that amisulpride in a lower dose range (50-400 mg/day) has shown antidepressant actions (7). However, amisulpride has never been explored in PSD. Amisulpride monotherapy might have the added advantage of avoiding polypharmacy in these patients.

Also, correlating the clinical findings with changes in serum Brain-Derived Neurotrophic Factor (BDNF), a neuro-biomarker constantly studied in depressive conditions, would help substantiate the results (8). In our present study on PSD, we would like to corroborate the efficacy of the interventions (low-dose amisulpride versus OFC) with the changes in serum levels of BDNF.

NULL HYPOTHESIS:

There is no difference in the change in the Calgary Depression Scale for Schizophrenia (CDSS) scores between the study groups over 8 weeks.

ALTERNATE HYPOTHESIS:

There is a difference in the change in the Calgary Depression Scale for Schizophrenia (CDSS) scores between the study groups over 8 weeks.

AIM:

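### The primary CDSS comparison makes no adjustment for baseline CDSS; using it as a covariate would usually gain precision for one degree of freedom

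*Combined protocol and SAP*

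**What the plan says.** Item 3 of the Statistical Analysis Plan is the only between-group analysis: "The means between the groups would be compared using unpaired t-test / Mann Whitney U test". No covariate, regression model or stratification factor is named anywhere in the document.

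Item 3 speaks of means, but other sections fix the quantity as change. The null hypothesis reads "There is no difference in the change in the Calgary Depression Scale for Schizophrenia (CDSS) scores between the study groups over 8 weeks", and the Follow Up section says that "the magnitude of the changes will be compared in-between the groups".

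Under Methodology, baseline values are available for all patients ("Then at baseline, the CDSS and CGI ratings would be assessed"), and there is one post-baseline assessment ("The two groups would be followed for 8 weeks, at the completion of which all the patients would be reassessed"). The Sample Size Calculation uses a difference of 3 CDSS points "with known SD of 3.8 and with a significant level 0.05 using a Two-sided Two-sample T-test", giving 26 per group, with 30 recruited to allow for attrition. Item 5 adds multiple imputation for the intention-to-treat analysis.

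**The concern.** A change score assumes that each extra point at baseline carries through as one extra point at week 8. The slope that makes best use of baseline is r × (week-8 SD ÷ baseline SD), which is usually not 1. When it is not, the change score keeps avoidable variance and corrects a chance baseline difference by the wrong amount.

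This matters more in a small trial. Only 26 completers per arm are planned, at about 80% power. The randomisation described has no stratification, and depression severity at entry is set by MADRS rather than CDSS, so nothing in the design balances baseline CDSS. At stake are the width of the confidence interval and the chance of detecting the planned 3-point difference. Bias and the type I error rate are not at stake.

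**Working it through.** **Inputs from the Sample Size Calculation:** difference 3, SD 3.8, two-sided 0.05, 26 per group (30 recruited).

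**Assumed, because not in the documents:** r = 0.3, 0.5, 0.7, and k = week-8 SD ÷ baseline SD = 0.75, 1, 1.25, 1.5. Both readings of 3.8 are taken in turn.

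**Step 1: the plan's own figure.** The standard error is 3.8 × √(2/26) = 1.054, so the noncentrality is 3/1.054 = 2.85. With 50 df the power is 79.7%. The normal approximation gives 81.2% and n = 26. The stated sample size reproduces.

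**Step 2: what adjustment does to the variance.** Write S for the baseline SD.

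- Variance of change: S²(1 + k² − 2rk)
- ANCOVA residual variance: S²k²(1 − r²)
- Difference between the two: S²(1 − rk)²

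The difference is never negative and is zero only when the slope rk equals 1. With k = 1 the ratio of ANCOVA to change-score variance is (1 + r)/2, a reduction of 35%, 25% and 15% at r = 0.3, 0.5 and 0.7.

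**Step 3: power if 3.8 is the SD of change.** The baseline SD is then 3.8/√(1 + k² − 2rk). ANCOVA has 49 df, and its variance is multiplied by 1 + 1/48 for the cost of estimating the slope. The change-score t-test has 79.7% power in every cell.

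| k | r = 0.3 | r = 0.5 | r = 0.7 |
|---|---|---|---|
| 0.75 | 98.3% | 96.9% | 95.8% |
| 1 | 92.9% | 89.0% | 85.0% |
| 1.25 | 87.7% | 83.2% | 79.6% |
| 1.5 | 84.1% | 80.3% | 79.0% |

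Simulation with the slope estimated (20,000 trials per cell) gave ANCOVA power from 79.0% to 98.2% and type I error from 4.8% to 5.2%.

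At k = 1 and r = 0.5 the residual SD is 3.8 × √0.75 = 3.29. The 95% CI half-width falls from 2.0086 × 3.8 × √(2/26) = 2.12 to 2.0096 × 3.29 × √(1 + 1/48) × √(2/26) = 1.85 points.

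**Step 4: power if 3.8 is the SD of the week-8 score.** The SD of change becomes 3.8 × √(1 + 1/k² − 2r/k), and the ANCOVA residual SD is 3.8 × √(1 − r²) whatever k is.

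| | r = 0.3 | r = 0.5 | r = 0.7 |
|---|---|---|---|
| Change-score t-test, k = 1 | 65.5% | 79.7% | 95.0% |
| ANCOVA | 82.5% | 89.0% | 97.2% |

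Over k = 0.75 to 1.5 the change-score test runs from 51% to 78% at r = 0.3 and from 83% to 97% at r = 0.7. On this reading the planned test can fall well short of 80%, while ANCOVA stays above it over the range shown.

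**Step 5: chance imbalance.** If the baseline SD is 3.8 (assumed), the baseline difference with 30 per arm has standard error 3.8 × √(2/30) = 0.98, and it exceeds 1 point in either direction in 31% of trials. The baseline SDs implied by the cells in Step 3 run from 2.48 to 5.31, which puts this probability between about 12% and 47%. A 1-point imbalance shifts the change-score estimate by 1 − rk, and a positive value favours the arm that starts worse. The shift is 0.5 point at k = 1 and r = 0.5, one-sixth of the design difference. Over the grid it runs from 0.78 to −0.05 point.

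**The case against.** The strongest reply is that nothing here is wrong. The hypotheses, objective and follow-up text all concern change, the trial is powered with the same kind of test, the stated 80% is met on the plan's own inputs, and the test is valid under randomisation. The gain cannot be fixed from the documents, and two cells in Step 3 are small net losses. Chance imbalance is already allowed for in the t-test's error rate, so Step 5 restates the efficiency point and is not a second harm. Item 3 itself says means, so comparing change is an inference. If week-8 means were compared without baseline, the fixed-slope argument would not apply.

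All of that stands as a limit on the claim, which is about efficiency only. It does not remove the case for changing the plan. The change reading is well supported by the null hypothesis and the Follow Up section. A comparison of raw week-8 means would ignore baseline altogether, so it too would forgo any gain from adjustment. Not knowing r favours ANCOVA, which estimates the slope where the plan assumes it. The two kinds of outcome are very uneven: a loss below one percentage point against a gain of up to about 19 points in Step 3.

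A fair question is why the plan offers a rank test and what happens if residuals are clearly non-normal. The slash in item 3 gives no rule for choosing, and the fix should supply one. That gap is minor and carries no weight in this conclusion.

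**Conclusion.** The point holds as a missed efficiency gain and should be acted on. The planned comparison is valid and its sample size reproduces, but it uses baseline CDSS with a slope fixed at 1 where the data could estimate it.

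The benefit is moderate to large where the slope of week-8 on baseline CDSS is well below 1, and close to nil where the slope is near 1. That range depends on the assumed r and SD ratio and on what 3.8 measures, none of which the documents state. Confidence in the direction is high; confidence in the size is limited.

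**What to change.** For the primary outcome, replace item 3 with text such as:

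> Week-8 CDSS will be compared between groups by ANCOVA with treatment group as factor and baseline CDSS as covariate, fitted in each imputed dataset and pooled. The adjusted mean difference with its 95% CI is the primary result. A Mann-Whitney test on change scores is a sensitivity analysis only.

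Taking change in CDSS as the outcome with the same covariate gives an identical adjusted difference, so the hypotheses and objective can stay as written. The ANCOVA estimate and standard error pool directly across the imputations in item 5. State how residuals will be checked, so that the role of the rank test is settled in advance.

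The same model can be used for CGI-S and serum BDNF, each with its own baseline value; no gain has been calculated for these. The Sample Size Calculation should also say whether 3.8 is the SD of change or of a score.

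The cost is a short SAP edit and one degree of freedom (50 to 49 at 26 per arm), which by itself moves power from 79.71% to 79.68%. The planned SPSS software can fit the model, and no extra patients, visits or data are needed. The change must be made before anyone sees unblinded outcome data; after that, ANCOVA belongs as a labelled sensitivity analysis.
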